5.8.9	Prior and Concomitant Medications	26
APPENDIX A - PROGRAMMING SPECIFICATIONS FOR TABLES AND LISTINGS		28
REFERENCES		30

1 Introduction

This Statistical Analysis Plan (SAP) describes the planned statistical analyses to be performed for data from Protocol AKST4290-211, “A Randomized, Double-Blind, Placebo-Controlled Study to Evaluate the Efficacy and Safety of AKST4290 in Subjects with Parkinson’s Disease (PD) on Stable Dopaminergic Treatment”. This SAP was created using Clinical Protocol AKST4290-211 Version 4.0 dated 22-MAY-2020. The table and listing shells will be provided in separate files as attachments to this SAP.

2 Objectives

2.1 Primary Objective

To assess the effects of AKST4290 on motor function in the practically defined off medication state, defined as ≥ 12 hours off levodopa, in subjects with PD.

2.2 Secondary Objectives

To assess the safety of AKST4290 in subjects with PD as well as the potential effects on clinical function and activities of daily living.

2.3 Exploratory Objectives

- To analyze pharmacokinetic parameters following twice daily dosing with AKST4290.
- To assess flow cytometry, pharmacogenomic, and biomarker evaluations conducted on blood and plasma samples.
- To assess bradykinesia, tremor, general activity, and sleep using a wearable device
- To evaluate fecal samples obtained at screening and following treatment for potential microbiome changes in consenting subjects.

3 Endpoints

3.1 Primary Endpoint

Change from Baseline (Day 1) in motor function during the practically defined off-medication state, defined as ≥ 12 hours off levodopa, at Week 12 (Day 84) as measured by Movement Disorder Society's Unified Parkinson's Disease Rating Scale (MDS-UPDRS), Part 3.

3.2 Secondary Endpoints

- Incidence of treatment-emergent adverse events (TEAEs) and serious adverse events (SAEs) identified by the Medical Dictionary for Regulatory Activities (MedDRA) preferred term (PT) and grouped by MedDRA System Organ Class (SOC).
- Incidence of abnormalities or clinically-significant changes from Baseline in laboratory test data, vital sign measurements, and electrocardiograms (ECGs).

- Change from Baseline (Day 1) in clinical function, motor function, and activities of daily living at Week 12 (Day 84) during the on-medication state as assessed by:
 - MDS-UPDRS Parts 1-4
 - Montreal Cognitive Assessment (MoCA)
 - Schwab and England Activities of Daily Living (SE-ADL) Scale
 - Clinical Impression of Severity Index – PD (CISI-PD)
 - PD Quality of Life Questionnaire-39 (PDQ-39)
 - Sheehan-Suicidality Tracking Scale (S-STS)
 - 10-meter timed walk (will also be assessed in the off-medication state)
 - Hauser 3-Day Patient Diary

3.3 Exploratory Endpoints

- Changes in concentration of AKST4290 or its major metabolites in plasma at various time points.
- Flow cytometric analyses and evaluation of pharmacogenomic characteristics and biomarkers in blood and plasma samples.
- Changes in bradykinesia, tremor, general activity, and sleep as measured by an FDA-cleared wearable sensor device.
- In consenting subjects (optional): characterization of the composition and function of the fecal gut microbiome.

4 Study Overview

4.1 Study Design

This is a phase 2, randomized, double-blind, placebo-controlled study to assess the efficacy and safety of AKST4290 in subjects with PD.

The study will enroll approximately 120 subjects between 50 and 80 years of age with a diagnosis of PD on dopaminergic treatment from approximately 30 sites globally. Enrolled subjects will be randomized in a 1:1 ratio to active treatment in Arm 1 (approximately 60 subjects) or placebo in Arm 2 (approximately 60 subjects). Subjects will take 400 mg of AKST4290 or placebo orally, twice per day (b.i.d.) for a total daily dose of 800 mg. The study duration for the subjects will be approximately 18 weeks including screening, 12 weeks of treatment, and 4 weeks of follow-up. A detailed overview of the timing of study assessments and interventions is presented in the Schedule of Events section below.

4.2 Treatment Assignment and Dose Regimen

A subject number will be assigned once the subject has signed the informed consent form. Enrolled subjects that have met all eligibility criteria will be randomized to AKST4290 (Arm 1: active dosing) or placebo (Arm 2: placebo dosing). The study drug will be self-administered orally b.i.d. (2 x 200 mg per dose), approximately 12 hours

apart, for a total daily dose of 800 mg. Subjects will receive study drug or placebo for a total of 12 weeks, followed by 4 weeks of follow-up.

4.3 Statistical Hypothesis

[figure not shown]
The null and alternative hypotheses for primary endpoint analysis are:

$$H_0: \mu_C = \mu_T \text{ vs. } H_A: \mu_C \neq \mu_T.$$

The null hypothesis is that there is no difference in mean change (μ) from baseline motor function during the practically defined off-medication state at Week 12 - as measured by the MDS-UPDRS Part 3 - between the control (C) and treated (T) groups. The alternative hypothesis is that there is a difference in mean change from baseline motor function during the practically defined off-medication state at Week 12 between the control and treated groups. P-values for testing whether the differences are equal to zero will be provided. P-values will be compared against an alpha significance level of 0.1.

4.4 Sample Size Justification

A total of approximately 120 subjects will be randomized in a 1:1 ratio to active treatment (approximately 60 subjects) or placebo (approximately 60 subjects), with the intent of obtaining ~108 evaluable subjects.

4.5 Randomization/Unblinding

This is a randomized and double-blind study.

4.5.1 Randomization

A randomization list, permuted blocks and stratified by sex (Male and Female) was generated by an outside vendor and is outside the scope of this SAP.

4.5.2 Unblinding

The study blind can be broken for safety reasons if the information is required for the management of SAEs, severe AEs, or pregnancies. The Investigator can obtain the treatment allocation for their subject through the web-based

randomization system (IRT). Else, the blinded code for the trial will be broken only after all subject data has been recorded and verified and the database locked.

4.6 Interim Analyses

Safety will be monitored on an ongoing basis, and a Safety Evaluation Meeting may be triggered (see protocol section 8.5). Any such ad hoc interim safety analysis performed will be outside the scope of this SAP.

4.7 Study Assessment Time Points

The study consists of 8 protocol-specified visits which will be assessed as nominal visits from an analysis perspective:

- Visit 1, Screening Visit (Day -14 to -7)
- Visit 2, Baseline (Day 1): Subjects will be randomized after eligibility has been confirmed, study drug/placebo dispensed.
- Visit 3 (Day 14 ± 2)
- Visit 4 (Day 28 ± 2)
- Visit 5 (Day 56 ± 2)
- Visit 6 – End of Treatment (EOT) (Day 84 ± 2)
- Visit 7 (Day 98 ± 3 or 14 days after Early Termination)
- Safety Follow-Up (Day 114 ± 2 or 30 days after Early Termination): a documented phone call to record AEs and concomitant medications (CMs).
- Early termination: In cases of early termination, if a subject has received at least 1 dose (400 mg) of AKST4290 or placebo, the site should try to perform all assessments scheduled at the Visit 6 - EOT visit as well as the subsequent follow up visits unless the subject has withdrawn consent.

4.8 Schedule of Events

Visit Number	1	2	3	4	5	6/EOT	7	Phone Call
Day	-14 to -7	1	14	28	56	84	98	114
Window (days) ^a			±2	±2	±2	±2	±3	±2
Week			2	4	8	12	14	15
Informed Consent ¹ /Optional Consent: fecal sample	X							
Demographics	X							
Medical history	X							
Inclusion/exclusion criteria	X	X						
Randomization to AKST4290 or placebo		X						
Modified Hoehn and Yahr	X							
Provide PDQ-39 to be completed prior to next visit	X	X	X	X	X	X		
Provide Hauser 3-Day Diary for next visit	X				X			
Confirmation of off-medication state		X		X		X	X	
Full physical examination	X							
Targeted physical examination		X	X	X	X	X	X	
Vital signs	X	X	X	X	X	X	X	
Laboratory tests	X	X	X	X	X	X	X	
Pregnancy testing ²	X	X	X	X	X	X	X	
12-lead ECG	X			X		X		
MDS-UPDRS Part 3 – Off-medication		X		X		X	X	
10-meter timed walk – Off-medication		X		X		X	X	
Administration of dopaminergic medication		X		X		X	X	
MDS-UPDRS Part 1-4 – On-medication		X	X	X	X	X	X	
10-meter timed walk – On-medication		X	X	X	X	X	X	
MoCA		X				X		
SE-ADL and CISI-PD		X	X	X	X	X	X	
S-STIS		X				X		

FM DM015.1

Statistical Analysis Plan
AKST4290-211

Rev B
Page 12 of 30

Collect PDQ-39		X	X	X	X	X	X	
Collect Hauser 3-Day Patient Diary		X				X		
Wearable sensor device ³	X	X		X	X	X		
Fecal sample (optional)	X					X		
Dispense 5-week supply of AKST4290/placebo		X		X	X			
Study agent administration ⁴		X	X	X	X	X		
Study agent accountability		X	X	X	X	X		
Pharmacokinetics blood sample ^{5,6}		X	X	X	X	X	X	
Biomarker plasma aliquots ^{5,6}		X				X	X	
FACS/CBC blood sample ⁵		X				X		
Pharmacogenomics blood sample (and optional DNA banking sample)		X						
Adverse events	X	X	X	X	X	X	X	X
Concomitant medications ⁷	X	X	X	X	X	X	X	X
Trial completion								X

Notes:

- a. Window extensions and missed protocol assessments may be permitted to reduce the risk of COVID-19 exposure. Any deviation to the protocol to reduce the risk of COVID-19 exposure will be captured as a “Protocol Deviation related to COVID-19” to categorize the anticipated increase in protocol deviations due to the pandemic. These measures are temporary, and will be repealed as soon as the situation (e.g., governmental rules, benefit/risk assessment for the trial, etc.) allows (see [Section 13.3](#)).
1. All patients must sign an informed consent consistent with ICH-GCP guidelines prior to any trial related procedures, which includes medication washouts and restrictions.

FM DM015.1

Statistical Analysis Plan

Rev B

AKST4290-211

Page 13 of 30

2. Pregnancy testing may be performed using serum or urine. Test should be performed at the site and results reviewed. Positive results should be confirmed by the central lab.
3. An at home wearable watch will be provided in clinic on Visits 1, 4 and 5. The watch will be collected at Visits 2, 5, and 6.
4. Study agent (AKST4290/placebo) will be self-administered in the clinic under supervision of study personnel during every visit of the treatment period (Visits 2-6). Training on study agent administration will be conducted at Visit 2. Study agent administration will be performed after all assessments during Visit 2 and at visit start at remaining visits (after collection of initial PK sample 15 minutes prior to study agent administration, if applicable). Please [Section 7.3](#) for timing dependencies.
5. The PK sample is drawn ~15 minutes prior to study agent (AKST4290/placebo) administration at Visits 2-6. Biomarker and FACS/CBC samples are drawn ~15 minutes prior to study agent (AKST4290/placebo) administration at Visits 2 and 6. The PK, biomarker, and FACS/CBC samples are drawn ~1 hour after study agent administration at Visit 2. Additional (optional) PK samples are drawn at ~ 2 hours after study agent administration at Visit 2. Additional (optional) PK samples are drawn at ~ 1 hour and ~ 2 hours after study agent administration at Visits 4 and 6. For additional information regarding timing, see [Section 17.12](#).
6. Biomarker plasma aliquots are drawn from the PK blood sample.
7. [REDACTED]

5 Statistical Methodology

5.1 General Considerations

This section presents the statistical approaches that are anticipated for the analysis of the study data. These approaches may at times require modifications due to unanticipated features of the data. Deviations from analyses summarized in this document will be noted in the clinical study report (CSR).

All statistical analyses will be performed using SAS® Version 9.4 or higher, unless otherwise noted. All summary statistics will be descriptive unless noted otherwise. Descriptive summaries will include mean, standard deviation (STD), median, and range for continuous variables and counts, and percentages for categorical variables. Two-sided 95% confidence intervals (CIs) will be provided for the means and percentages as needed. For key outcome measures, the difference between the treatment arms and the 95% CI of the difference will be computed, as necessary. Presentations will be by treatment group, unless otherwise noted.

In general, all summary tables will be supported by a relevant subject data listing including all subjects who are randomized. The listings will include all data collected, and will be sorted by subject ID, and actual visit date, as applicable, unless otherwise noted.

Concomitant medications will be coded by the World Health Organization (WHO) Drug Dictionary and adverse events and medical history will be coded using the MedDRA. The dictionary versions will be documented in the Data Management Plan for the study.

Study day 1 is the first day of study treatment. Study day is the day relative to the study day 1. Baseline is the last non-missing valid value prior to study treatment.

5.2 Study Populations for Analysis

5.2.1 Intention-to-Treat (ITT) Population

All subjects who were randomized into the study will be included in the ITT population. Analysis will be done according to the treatment subjects were randomized to.

5.2.2 Modified Intention-to-Treat (mITT)/Evaluable Population

The mITT/evaluable population will be a subset of the ITT population that only includes subjects with non-missing baseline and Week 12 (Day 84) values for off-medication motor function as measured by the MDS-UPDRS Part 3. Analysis will be done according to the treatment subjects were randomized to.

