5.6 Methods for Handling Missing Data

In order to minimize missing data, every effort will be made to obtain required data for all randomized subjects at each scheduled evaluation. However, in the event that more than 5% of data are missing, imputation methods will be used for analysis of the primary endpoint only. The imputation will be carried out in SAS version 9.4 or later using PROC MI.

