5.7.1 Primary Efficacy Endpoint

The primary endpoint is change from baseline at Week 12 (Day 84) in the off-medication motor function as measured by the MDS-UPDRS Part 3. The main analysis for the primary efficacy variable will be analyzed using mITT subjects.

The MDS-UPDRS (Fahn, 1987; Goetz, 2008) was developed to incorporate elements from existing scales to provide a comprehensive but efficient and flexible means to monitor PD-related disability and impairment. The MDS-UPDRS has four components (Part 1, Mentation, Behavior, and Mood; Part 2, Activities of Daily Living; Part 3, Motor; Part 4, Complications). The rating for each item is from 0 (normal) to 4 (severe). The score for each Part is obtained from the sum of the corresponding item scores.

The null and alternative hypotheses for the primary endpoint are:

$$H_0: \mu_C = \mu_T \text{ vs. } H_A: \mu_C \neq \mu_T.$$

The null hypothesis states that there is no difference in mean change (μ) from baseline motor function during the practically defined off-medication state at Week 12 - as measured by the MDS-UPDRS Part 3 - between the control (C) and treated (T) groups. The alternative hypothesis states that there is a difference in mean change from baseline motor function during the practically defined off-medication state at Week 12 between the control and treated groups.

The MDS-UPDRS Part 3 is administered in the off-medication state at Baseline (Study Day 1) and Weeks 4 (Day 28), 12 (Day 84), and 14 (Day 98). The sum of corresponding items for section 3 will be summarized descriptively at each scheduled visit. Additionally, the number and percentage of subjects with dyskinesia present during the evaluation, and whether that dyskinesia interfered with ratings, will be presented.

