A mixed-effect model for repeated measures (MMRM) will be employed to analyze the change from baseline scores at each visit over time up to Week 12. The model will include the fixed effects of treatment (stratified, by sex), baseline of the endpoint, visit, and treatment by visit interaction. An unstructured covariance structure will be used to model the within subject error. Least-square (LS) means, standard error (SE), and 95% CI of the LS mean will be provided for each treatment arm at each visit. The unadjusted mean change from baseline, and the difference in LS means between treatment arms and 95% CI of the difference will also be calculated. P-value for testing whether the difference is equal to zero will be provided. The p-value at Week 12 will be compared against the alpha significance level of 0.1.

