5.7.1.1 Sensitivity Analyses

The main analysis of the primary endpoint using the above MMRM will use all available data. To check the robustness of the results, the following sensitivity analyses will be performed:

FM DM015.1
Statistical Analysis Plan
AKST4290-211

Rev B
Page 18 of 30

- Analysis of covariance (ANCOVA) model on the observed change from baseline value at Week 12. The model includes treatment as the fixed effect and baseline of the endpoint as a covariate.
- The same MMRM model on data from the PP subjects.
- The same MMRM model on data from the ITT subjects.
- Depending on the status of missing data among the mITT population, multiple imputations may be employed to handle missing data and apply the MMRM on the imputed datasets. See Methods for Handling Missing Data section (section 5.6) for details on imputation methods.

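### The primary test at 0.10 uses only subjects with a Week 12 score, so the MMRM is close to a completer analysis, and imputation is tied to that same set

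*SAP*

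**What the plan says.** Section 5.2.2 restricts mITT/Evaluable to a subset of ITT that "only includes subjects with non-missing baseline and Week 12 (Day 84) values for off-medication motor function". Section 5.7.1 then states: "The main analysis for the primary efficacy variable will be analyzed using mITT subjects". The model is an MMRM of change from baseline up to Week 12 with unstructured covariance, and "The p-value at Week 12 will be compared against the alpha significance level of 0.1". The same section and the schedule in 4.8 place off-medication Part 3 at baseline and Weeks 4, 12 and 14.

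Section 5.7.1.1 says: "The main analysis of the primary endpoint using the above MMRM will use all available data". It lists four sensitivity analyses: an ANCOVA on observed Week 12 change, the MMRM in the PP set, "The same MMRM model on data from the ITT subjects", and a conditional imputation: "Depending on the status of missing data among the mITT population, multiple imputations may be employed to handle missing data". Section 5.6 sets the trigger: "in the event that more than 5% of data are missing, imputation methods will be used for analysis of the primary endpoint only". Section 4.4 plans about 120 randomized subjects to yield about 108 evaluable ones.

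**The concern.** Membership of the primary set depends on something that happens after randomization, namely whether the Week 12 score was obtained. An MMRM is normally preferred to an ANCOVA because it uses partial records from subjects who lack the final value. Section 5.2.2 removes exactly those subjects, so the statement that all available data are used holds only inside the reduced set.

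The safeguard misses its target. Imputation is directed at missing data in mITT, where the endpoint is complete by definition. The ANCOVA needs an observed Week 12 value, and the PP set requires complete Week 12 assessments. Only the ITT MMRM clearly admits a subject without a Week 12 score, and it does not supply the primary p-value.

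If loss of the Week 12 score is related to outcome, and the relation or the rate differs between arms, the primary estimate is biased and the true type I error can exceed 0.10.

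**Working it through.** **1. What can be missing in the primary set.** The post-baseline visits in the model are Weeks 4 and 12. Week 12 is present for every mITT member, so only Week 4 can be absent.

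**2. How many subjects are left out (4.4).** 120 − 108 = 12, and 12/120 = 10%. As a check, 108/0.90 = 120. The loss is implied by these figures; the SAP states no dropout rate.

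**3. The 5% trigger (5.6).** The sentence names no set or denominator.
- Week 12 values missing within mITT: 0 of about 108, so it can never be met.
- Randomized subjects without Week 12: 5% of 120 is 6, so 7 or more meets it, and the implied 12 would.

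**4. How close the mITT MMRM is to a completer ANCOVA.** Two sets of simulated trials were run, each assuming 3% sporadic missing Week 4 scores. The two Week 12 estimates correlated 0.986 to 0.996. In the set with a Week 4 to Week 12 correlation of 0.6, their biases agreed within 0.001 SD.

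**5. Bias by hand.** Suppose a fraction p of an arm is lost and those lost average m SD worse at Week 12. The arm's completer mean shifts by −m·p/(1−p). With the same m in both arms, the bias is m·[p₁/(1−p₁) − p₂/(1−p₂)].
- 15% against 5%: 0.1765 − 0.0526 = 0.124 SD per SD of m.
- 7.5% against 2.5%: 0.0811 − 0.0256 = 0.055.
- Equal rates: 0.

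**6. Simulation.** Assumptions, none from the SAP: 60 per arm, no true effect, standardized normal scores, Week 4 to Week 12 correlation 0.5 to 0.7, logistic dropout with slope 0.5 to 1.5 per SD, 20,000 trials per setting. Bias is in absolute SD units. The ITT MMRM range covers every lost subject having a Week 4 score through to half of them lacking it.

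| Loss | Slope | Completer bias | Completer type I | ITT MMRM |
|---|---|---|---|---|
| Random, or same mechanism and rate | – | about 0 | 0.10 | about 0 |
| Driven by Week 4, 15%/5% | 0.5 | 0.02–0.03 | about 0.10 | about 0, to half the bias |
| Driven by Week 4, 15%/5%, or outcome-related in one arm only at 10%/10% | 1.0–1.5 | 0.04–0.09 | 0.11–0.13 | about 0, to half the bias |
| Driven by unseen Week 12, 15%/5% | 0.5 | 0.05 | 0.11 | 0.02–0.04; type I 0.10–0.11 |
| Same | 1.0 | 0.08–0.09 | 0.13 | 0.04–0.07; type I 0.11–0.13 |
| Same | 1.5 | 0.11 | 0.16 | 0.06–0.10; type I 0.11–0.15 |
| Half the loss, 7.5%/2.5% | 1.0–1.5 | 0.02–0.06 | 0.10–0.12 | – |

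Mechanisms running in opposite directions by arm are an extreme case. If driven by Week 4, they give 0.09–0.17 SD and type I error 0.14–0.23. If driven by Week 12 at slope 1.0, they give 0.18 SD and 0.25–0.26. A repeat with 8,000 trials per setting agreed within simulation noise, except for one setting at 0.142 against 0.13.

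**7. Cross-check of type I error.** With 54 per arm, SE = √(2/54) = 0.192 SD. For bias b, set d = b/0.192; then type I error ≈ Φ(−1.645 + d) + Φ(−1.645 − d).
- b = 0.05: d = 0.26, giving 0.11.
- b = 0.09: d = 0.47, giving 0.14.
- b = 0.11: d = 0.57, giving 0.155.

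These agree with the table to within about 0.01. For scale, the effect detectable with 80% power at two-sided 0.10 is (1.645 + 0.842) × 0.192 = 0.48 SD.

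**The case against.** **The better analysis is already planned.** The ITT MMRM is listed without condition, and the revision history shows ITT added to the efficacy tables. No data are lost to the plan, and a disagreement would be visible. This stands, but the result tested at 0.10 is still the mITT one.

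**The trigger can be read sensibly.** The sentence before it in 5.6 speaks of obtaining data for all randomized subjects, which favours the 7-of-120 reading. That is a fair reading, but the trigger itself names no set. Section 5.7.1.1 points to mITT and makes imputation optional, where 5.6 makes it definite. The two sections still have to be reconciled.

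**The effect may be small.** It is nil for random loss or loss alike in both arms. It is 0.02 to 0.03 SD for a weak mechanism driven by Week 4, against an SE of about 0.19 SD. Nothing in the SAP suggests differential loss, and the extreme cases should carry little weight. This stands.

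**The set may be wider than it looks.** Section 4.7 asks sites to attempt the end-of-treatment assessments at early termination. If those scores count as Week 12, fewer subjects drop out of mITT, as in the half-loss row. The SAP does not say whether they count.

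**The remedy is partial.** If loss depends on the unseen Week 12 score, the ITT MMRM keeps 50–77% of the bias when every lost subject has a Week 4 score, and 73–88% when half do not. Imputation under missing at random shares that limit. This stands too, but in these settings the ITT MMRM still has the smaller bias.

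**Conclusion.** The concern holds. That the primary MMRM is in effect a Week 12 completer analysis, and that imputation is aimed at a set with no missing endpoint, follows from the SAP's own text without any assumption.

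The size of the consequence does rest on assumptions. For outcome-related loss of 15% against 5%, the bias is about 0.02 to 0.11 SD and the type I error 0.10 to 0.16. With random loss, or loss alike in both arms, there is no bias. The direction cannot be known from the SAP. This should be fixed before unblinding, because the effect is conditional but the defect is certain and the repair is cheap.

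**What to change.** 1. In 5.7.1, make the ITT MMRM from 5.7.1.1 the main analysis, using every observed off-medication Part 3 value at Weeks 4 and 12.
2. Keep the present mITT/Evaluable set as a completer sensitivity analysis.
3. In 5.6 and 5.7.1.1, apply multiple imputation to the ITT set, count the 5% trigger as randomized subjects without a Week 12 value, and state once whether imputation is mandatory or optional.
4. State how early-termination assessments (4.7) map to Week 12, since this decides how many subjects are affected.
5. Align the population sentence in 5.7, which names only mITT/Evaluable and PP, with 5.7.1.1 and 5.7.2, which also use ITT.

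The cost is SAP rewording before unblinding and running the imputation on the ITT set, with no new data or subjects. The protocol (Version 4.0) is not at hand; if it fixes the primary set, it must be aligned as well. The new main analysis assumes missing at random, recovers little for subjects lost before Week 4, and removes only 12–50% of the bias when loss depends on the unseen Week 12 score.
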